1.0 Study Summary

Study Title	MEND 2: Making Treatment Decisions Using Genomic Testing
Study Design	Single Arm Feasibility and Efficacy Study
Primary Objective	
• Examine intervention feasibility via patient and oncologist acceptability, recruitment and retention, and fidelity
Secondary Objective(s)	
• Evaluate intervention effects on comprehension and treatment preferences.• Assess potential intervention mechanisms on comprehension, preferences, and satisfaction.
Research Intervention(s)/Investigational Agent(s)	Two surveys and audio recordings of patient-physician encounter using the question prompt list.
IND/IDE #	N/A
Study Population	Patients
Sample Size	75
Study Duration for individual participants	About a month, depending on appointment schedule.
Study Specific Abbreviations/Definitions	QPL: Question Prompt List HER2: Human Epidermal Growth Factor Receptor 2 ER: Estrogen Receptor PR: Progesterone Receptor LCCC: Lombardi Comprehensive Cancer Center WHC: Cancer Institute at Washington Hospital Center MCC: H. Lee Moffitt Comprehensive Cancer Center

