2.0 Objectives*

2.1 Specific Aims.

- Specific Aim 1: Examine intervention feasibility in 3 areas: 1) patient and oncologist acceptability, 2) participant recruitment and retention, and 3) intervention dosage and fidelity.
- Specific Aim 2: Evaluate intervention effects on comprehension and treatment preferences.
- Specific Aim 3: Assess potential intervention mechanisms on comprehension, preferences, and satisfaction.

2.2 Hypotheses/Research questions.

- Aim 2 Hypothesis: Participants will demonstrate significant increases in comprehension about their disease and its treatments from pre- to post-QPL. Participants will be more likely to report Score-concordant preferences from pre to post-QPL.
- Aim 3 Hypothesis: Patient comprehension and satisfaction will be higher following encounters with greater shared decision making, greater perceived communication quality, and more frequent discussion of risks/benefits of treatments. Patient preferences will likely be more Score-concordant following encounters with greater shared decision making, greater perceived communication quality, and more frequent discussion of risks/benefits of treatments.

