3.0 Background*

Breast cancer is the most common cancer among US women, with more than 230,000 new diagnoses and 40,000 deaths each year,¹ along with decrements in quality of life.² Half of all newly-diagnosed patients are affected with estrogen-receptor positive, early-stage disease. Clinical guidelines for these women integrate genomic tumor profiling tests such as the Oncotype DX® Recurrence Score to refine recurrence estimates and systemic therapy selection when combined with existing markers. Thousands of women receive testing each year.³⁻⁵ While these women should all receive hormonal therapy, guidelines suggest that the 25% with a high Score benefit from additional chemotherapy and the 50% with a low Score can safely avoid chemotherapy.⁶ Appropriate treatment for the 25% of women with intermediate Recurrence Scores remains unclear until clinical trial (TAILORx) results are released in the next year.⁷

Despite continuing dissemination, many challenges remain to maximize the benefits offered by testing and refined treatment selection. Many women have a poor understanding of their

PROTOCOL TITLE:
Making Treatment Decisions Using Genomic Testing

Recurrence Score and its impact of treatment selection.⁸ Further, our data suggest that patients' pretesting preferences do not shift following the receipt of their Recurrence Score, even following discussion of test results that should guide treatment selection. These preferences are a powerful driver of treatment utilization, predicting treatment received over and above the effect of the Recurrence Score and other clinical variables. Indeed, many patients do not receive Score-concordant care.^{4,9-11} Finally, tested patients who do not take an active role in their care and report poorer communication by their oncologist are at risk for higher distress and poorer quality of life.¹² Our data suggest a need to test interventions that support communication about the Recurrence Score, improving patient comprehension and better aligning patient preferences with evidence-based recommendations, ultimately impacting patient morbidity and mortality. TAILORx results will continue to strengthen the evidence for clinical utility and increase testing rates. An effective intervention should be ready to respond to this increasing need.

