Street et al.'s model of patient-centered communication¹³ suggests pathways through which clinical communication has indirect effects on morbidity and mortality. Communication can influence more proximal outcomes, including patient comprehension of their disease and its treatments, treatment preferences and satisfaction, involvement in care decisions as well as longer-term outcomes of treatment adherence and quality of life.¹⁴ We aim to test the feasibility and impact of a patient activation intervention to support effective integration of the Recurrence Score into clinical encounters and treatment decisions. Patient activation interventions utilizing a question prompt list (QPL) can impact proximal outcomes of preferences, comprehension, satisfaction and involvement.¹⁵⁻¹⁸ A QPL could allow tested patients to better understand the rationale for their oncologist's treatment recommendation and its impact on the management of their disease, as well as encourage alignment of treatment preferences, the Recurrence Score and treatment selection. In this trial, we will recruit newly-diagnosed breast cancer patients to a single-arm trial to demonstrate feasibility and preliminarily assess the impact of the QPL on key outcomes.

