Comprehension	Adjuvant treatment, Recurrence Score, treatment implications	X		X
Coding of clinical encounters	RS- and treatment related information, shared decision making, patient active participation and patient-centered communication		X	X
Decisional Satisfaction	SDS			X
Communication Quality	Makoul et al.			X

Chemotherapy Preferences. We will assess preferences for chemotherapy by assessing the perceived pros (8 items) and cons (8 items) of treatment as we do in our ongoing work. Women rate the importance of each item on a scale from 1 (*Not at all important*) to 4 (*Very important*). Ratings are averaged to create scales, with higher scores indicating greater importance of pros and cons. Internal reliability is high for pros-cons, with scores above zero indicating a preference for chemotherapy. Preference concordance will be determined through a match between post-Score preference and treatment received.

Comprehension. We will assess comprehension of adjuvant treatment, Recurrence Score and category, and treatment implications (*The Test helps women decide about chemotherapy (Y/N)*). We will apply existing comprehension items, in which patients average 70% correct.¹⁴

Satisfaction. We will assess Decisional Satisfaction with the valid and reliable 6-item Satisfaction with Decision Scale, rated on a 5-point Likert scale (*Strongly agree/ disagree*), with a higher score indicating greater satisfaction. The measure has been used to assess satisfaction with breast cancer adjuvant treatment decisions.¹⁹

Perceived communication quality. We will assess patients' perceptions of quality of patient-physician communication using a 7-item scale from 1 (*Very strongly disagree*) to 6 (*Very strongly agree*). This scale has good reliability and validity and we have used this measure in our current observational study. Items are relevant to chemotherapy decisions (*The doctor fully explained the risks of treatment recommended*). Patients will respond to these regarding their primary Medical Oncologist.²⁰

Oncologist variables. We will record race, ethnicity, and gender of the patient's primary medical oncologist for our measurement of concordance.

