26.0 Multi-Site Research*

26.1 Study-Wide Number of Subjects*

We very conservatively project 60 eligible participants per year from LCCC/WHC and 120 eligible participants per year at MCC.

26.2 *Subjects will be recruited according to methods under the control of the local site. Sites will have bi-monthly meetings to discuss strategies and any issues as they arise.*

PROTOCOL TITLE:
Making Treatment Decisions Using Genomic Testing

References

6. NCCN Clinical Practice Guidelines. Breast Cancer. Version 4.2024 [Internet]. Available from: https://www.nccn.org/professionals/physician_gls/pdf/breast.pdf

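### The plan's only preference-concordance rule leaves out the Recurrence Score and has no T1 value, so Score-concordant preference, the outcome named in Aims 2 and 3, has no working definition

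*Combined protocol and SAP*

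**What the plan says.** Section 2.2 states the second Aim 2 hypothesis as "Participants will be more likely to report Score-concordant preferences from pre to post-QPL". For Aim 3 it states "Patient preferences will likely be more Score-concordant following encounters with greater shared decision making", and adds perceived communication quality and discussion of risks and benefits as further predictors. Both fall under secondary objectives in section 1.0, the first of which is "Evaluate intervention effects on comprehension and treatment preferences".

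Section 6.4 scores preference as the mean rating of eight pros minus the mean rating of eight cons, and reads a value above zero as preferring chemotherapy. It then gives the plan's one rule for concordance of preference: "Preference concordance will be determined through a match between post-Score preference and treatment received". Table 1 schedules preference at T1 and T2, but the Recurrence Score and chemotherapy selection at T2 only. By section 6.2, T1 comes before the woman has her result.

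Section 3.0 gives a direction for two of the three Score categories: "guidelines suggest that the 25% with a high Score benefit from additional chemotherapy and the 50% with a low Score can safely avoid chemotherapy". For intermediate Scores, a further 25%, it says that the appropriate treatment "remains unclear until clinical trial (TAILORx) results are released in the next year".

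Section 17.1 plans mixed models with patient and oncologist random terms and a fixed term for time. It names comprehension as the outcome of the linear model 2a. The adjusted odds ratio that follows has no named outcome.

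**The concern.** The hypotheses concern whether a woman's preference matches what her Score indicates, and for Aim 2 whether that match becomes more common. The rule in section 6.4 concerns whether her preference after the Score matches the treatment she received. That is a different question, asked at one time point.

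An analyst who applies section 6.4 literally will have no pre-post outcome for one of the two Aim 2 hypotheses. For Aim 3 the analyst will report an association with preference-treatment agreement under the name of Score-concordance. An analyst who sets section 6.4 aside must build the outcome alone, including the treatment of intermediate Scores, possibly after seeing the data.

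**Working it through.** **1. The plan's own figure.** Inputs from section 17.1: 75 women at T2, 10 patients per oncologist, ICC 0.02. Design factor = 1 + (10 − 1) × 0.02 = 1.18. Effective N = 75 / 1.18 = 63.6, which reproduces the stated 64. The stated power is for comprehension; none is given for preference.

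**2. What each outcome needs, against what the rule uses.**

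| | Preference at T1 | Preference at T2 | Score category | Treatment received |
|---|---|---|---|---|
| Aim 2 hypothesis | yes | yes | yes | no |
| Aim 3, preference part | no | yes | yes | no |
| Rule in section 6.4 | no | yes | no | yes |
| Collected (section 6.4, Table 1) | yes | yes | yes | yes |

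Everything the hypotheses need is collected. The rule does not combine the right columns.

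**3. Aim 2.** Before the result is known there is no post-Score preference, so the rule yields one value per woman where a pre-post model needs two. With T2 values only, the time effect in the section 17.1 model cannot be estimated, and the patient random effect is not identified.

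**4. Aim 3.** No T1 value is needed, but the construct changes. For a woman with a high or low Score, let P be her T2 preference, T the treatment received and D the direction in section 3.0, each coded chemotherapy or none.

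- Section 6.4 rule: concordant if P = T.
- Score-concordance: concordant if P = D.
- If T = D, the two conditions are identical.
- If T ≠ D, P equals exactly one of T and D, so the two always give opposite answers.

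For example, a low-Score woman who prefers and receives chemotherapy is concordant under section 6.4 but not Score-concordant. A high-Score woman who prefers chemotherapy and does not receive it is the reverse. Section 3.0 says that care at odds with the Score is common but gives no rate, so the number of women affected cannot be worked out. For intermediate Scores section 3.0 gives no D, yet the section 6.4 rule still returns a value.

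**5. Is the outcome defined elsewhere?** Section 3.0 supplies D for high and low Scores as background, section 6.4 supplies the cut-off for preference, and Table 1 supplies the data. No section joins them into an outcome at T1 and T2 or says what happens to intermediate Scores.

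**6. Cost of leaving intermediate Scores out.** Assumption: the 25% in section 3.0 holds in this sample.

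- Women leaving: 75 × 0.25 = 18.75, about 19.
- Women remaining: 75 × 0.75 = 56.25.
- Effective N at 10 per oncologist: 56.25 / 1.18 = 47.7.
- Effective N if cluster size also falls by a quarter, to 7.5: factor 1 + 6.5 × 0.02 = 1.13, and 56.25 / 1.13 = 49.8.

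Effective N is therefore about 48 to 50 instead of 64.

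**The case against.** The strongest reply is that section 6.4 defines preference concordance, section 2.2 speaks of Score-concordant preferences, and nothing says that the first operationalises the second. The match could be a measure in its own right: the secondary objective on treatment preferences is broad enough to hold it, and section 3.0 says that a QPL could "encourage alignment of treatment preferences, the Recurrence Score and treatment selection". Much of the missing definition can also be inferred, since direction, cut-off and data are all present for high and low Scores.

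The first part stands as a limit. A reader might infer that the plan commits Aims 2 and 3 to the wrong measure; the documents do not tie the rule to them explicitly, so that failure is conditional on the rule being used. But the benign reading does not rescue the plan. It leaves the named outcome with no explicit definition, and the odds ratio with no outcome. Inference covers high and low Scores only.

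Two other stronger readings fail. A reader might say that a preference of exactly zero is unclassified. Section 6.4 requires a value above zero for a chemotherapy preference, so zero is not one. A reader might also take the loss of about 19 women as the size of the defect. It is the cost of one remedy.

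**Conclusion.** The point holds and should be fixed before analysis. Either the section 6.4 match is the Aim 2 and 3 outcome, in which case it cannot show the Aim 2 change and gives Aim 3 a different construct, or it is a separate measure and the outcome is not explicitly defined.

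The effect is structural. A reader might infer that the results will be biased, or biased in favour of the QPL. The documents do not support that, because without a rate of Score-discordant treatment neither size nor direction can be stated. The aims are secondary in a feasibility study, and the comprehension hypothesis is untouched. The conclusion on the construct rests on taking the directions in section 3.0 as what Score-concordant means for high and low Scores.

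**What to change.** In section 6.4, define Score-concordant preference at T1 and at T2 as agreement between the recorded pros-minus-cons preference (above zero = prefers chemotherapy, otherwise not) and the direction that section 3.0 gives for the recorded high or low Score category. State in advance that women with intermediate Scores are left out of this binary outcome and kept in a supporting model of the continuous pros-minus-cons score, unless the sponsor first reconciles section 3.0 so that it gives a direction.

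In section 17.1, name this indicator as the outcome of the adjusted odds ratio, and use its T2 value for Aim 3. Report the existing match separately under its own name, such as *preference-treatment agreement*.

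This costs wording only, since every component is already collected. There are two downsides. T1 preference is scored against a Score not yet disclosed, so the pre-post change reflects Score disclosure together with the QPL, and the report should say so. Leaving out intermediate Scores also lowers the precision of the binary analysis, to the effective N shown in the last step of the working.

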6.0 Procedures Involved*

PROTOCOL TITLE:

Making Treatment Decisions Using Genomic Testing

6.1 This is a feasibility and efficacy study. Two participant interviews will be conducted by the study staff. Audio recordings will be collected of patient-physician encounters using the QPL over a month time span.

6.2 Eligible patients will be contacted by study staff via phone call. The study staff will describe the study, answer questions, obtain verbal consent, and complete the first, T1 interview before the patient receives *Oncotype DX* results. After obtaining a signed informed consent and HIPAA authorization by mail, the QPL will be provided to the patient. They will receive the QPL by mail or email, depending on their preference, before their Score disclosure appointment. Study staff will be available to audio record the patient-physician encounter during their appointment. The second, T2 interview will be done after patients receive their test results but prior to initiation of adjuvant chemotherapy.

6.3 The risks of participation are minimal. The survey elements have been designed to minimize emotional distress. A distress protocol has been put in place to refer subjects to psychological consult when appropriate. It is possible that participants will derive benefit from the use of the QPL in how they communicate with their physician and make decisions regarding treatment options.

6.4 Measures will include:

Sociodemographics. We will assess age, race/ethnicity, education, marital, employment, income, insurance status, comorbidity, and family cancer history.

Disease variables and treatments. We will assess diagnosis date, pathology (staging, grade, ER/PR/HER2), treatments, and dates.

Oncotype DX Recurrence Score. We will assess the Recurrence Score and the related category.

Chemotherapy Selection. In our work, 95% of women make definitive treatment decisions by T2. If not, this will be noted and the interview will continue. *Data will be confirmed in the medical record.*

Self-Reported Measures:

Table 1. Variables and Data Sources		Timepoint		
Variable	Measure/source	T1	Encounter	T2
Controlling and Clinical Variables				
Sociodemographics		X		
Disease Variables, Treatments	Self-report and chart review	X		X
Recurrence Score	Self-report and chart review			X
Outcomes and Mediators				
Chemo. Selection	Self-report and chart review			X

PROTOCOL TITLE:
Making Treatment Decisions Using Genomic Testing

Chemo. Preferences	Preferences	X		X

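### About 95% of women are expected to have chosen treatment by T2, so the T2 preference score may reflect that choice, and its match with treatment cannot show that preferences were aligned beforehand.

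*Combined protocol and SAP*

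**What the plan says.** All references are to the combined protocol and SAP.

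- **Timing (6.2).** T1 is completed before the Oncotype DX result. For T2: "The second, T2 interview will be done after patients receive their test results but prior to initiation of adjuvant chemotherapy". The start of chemotherapy is the only later limit; T2 is not required to precede the decision.
- **Decision status at T2 (6.4, Chemotherapy Selection).** "In our work, 95% of women make definitive treatment decisions by T2". For the rest: "If not, this will be noted and the interview will continue". No analysis separates these women.
- **Preference measure (6.4 and Table 1).** Women rate the importance of 8 pros and 8 cons of chemotherapy, at T1 and T2 only. The score is the difference of the two means: "Internal reliability is high for pros-cons, with scores above zero indicating a preference for chemotherapy". Chemotherapy selection is a separate T2 item, confirmed in the chart.
- **Concordance (6.4).** "Preference concordance will be determined through a match between post-Score preference and treatment received".
- **Aim 2 hypothesis (2.2).** "Participants will be more likely to report Score-concordant preferences from pre to post-QPL". The preference part of the Aim 3 hypothesis also concerns Score-concordance.
- **Role of preference (3.0).** "These preferences are a powerful driver of treatment utilization, predicting treatment received over and above the effect of the Recurrence Score". The sentence just before this reports that, in the team's data, preferences held before testing stayed the same once the Score had been received and discussed.

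**The concern.** The Background treats preference as something that comes before the treatment choice and drives it. To see whether preferences were better aligned, one needs a preference taken after the question prompt list and the Score but before the choice. The plan has none. T1 precedes the Score, and T2 follows the decision for nearly everyone. The plan also gives the Satisfaction with Decision Scale at T2, which fits an interview held after the decision.

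A woman who has agreed to chemotherapy may rate its pros higher afterwards, and one who has declined may rate its cons higher. The T2 rating would then agree with treatment more often than the preference that went into the decision did. A woman whose preference never moved, but who accepted a Score-based recommendation and later rated in line with it, would count as concordant. With a single arm, no comparison group removes this from the T1-to-T2 change. At stake is whether the match can be read as preference guiding treatment, when it could equally be treatment guiding the rating.

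**Working it through.** **1. The plan's own figures.** The 95% is an empirical figure from earlier work and cannot be re-derived. The effective sample size in 17.1 reproduces: design effect 1 + (10 − 1) × 0.02 = 1.18, and 75 / 1.18 = 63.6, given as 64. It is stated for comprehension; no power is given for any preference outcome.

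**2. Women who have decided at T2.** 0.95 × 75 = 71.25, about 71 women. 0.05 × 75 = 3.75, about 4 women. Four cannot support a comparison of decided with undecided women.

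**3. Possible inflation of the match (illustration).** Let m be the true match between pre-decision preference and treatment, and f the share of mismatched, decided women whose T2 rating moves to fit the choice. The documents give neither value. Then

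observed match = 0.95 × [m + f(1 − m)] + 0.05 × m = m + 0.95 × f × (1 − m).

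| m | f = 0 | f = 0.10 | f = 0.25 | f = 0.50 |
|---|---|---|---|---|
| 60% | 60% | 64% | 70% | 79% |
| 70% | 70% | 73% | 77% | 84% |
| 80% | 80% | 82% | 85% | 90% |

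For example, m = 0.70 and f = 0.25 gives 0.70 + 0.95 × 0.25 × 0.30 = 0.771. At f = 0 the bias is zero.

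**4. The indirect route to Score-concordance (illustration).** Assume a standardised preference unrelated to the Score (50% concordant at T1), decisions that follow the Score with probability q, and ratings that move d SD toward the option chosen in the 95% who have decided. Then

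T2 Score-concordance = 0.5 + 0.95 × (2q − 1) × [Φ(d) − 0.5],

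with Φ(0.25) = 0.599 and Φ(0.5) = 0.691.

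| q | d = 0 | d = 0.25 | d = 0.5 |
|---|---|---|---|
| 0.8 | 50% | 56% | 61% |
| 0.9 | 50% | 58% | 65% |

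Simulating this model with effective N = 64, a T1–T2 correlation of 0.5 (which the plan assumes for comprehension only) and a two-sided McNemar test without continuity correction gives a significant T1-to-T2 change in roughly 12% to 19% of trials at d = 0.25 and 32% to 52% at d = 0.5, against a nominal 5%. Here q, d and the independence of preference and choice are all assumed. The independence is a simplification, because the Background says preference predicts treatment beyond the Score.

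**The case against.** The strongest points on the other side are these.

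- **The rating is not a report of the choice.** It is built from 16 importance items, and selection is recorded separately. A reader might infer that the T2 score simply measures a choice already made, or that its match with treatment is partly built in. The documents show neither. This stands: only *may reflect* and *may be inflated* are supported.
- **The team's own evidence points against a large effect.** If ratings moved well toward the chosen option, and most choices followed the Score, some shift would be expected in the earlier data; the Background reports none. This stands as a limit on the likely size. It does not settle the matter. The Background does not say when those ratings were taken relative to decisions, nor whether the absence of a shift is an average, which could hide women who chose and women who declined moving in opposite directions.
- **The hypotheses name a different outcome.** Section 2.2 concerns agreement with the Score, not with treatment received. This stands: the effect on those hypotheses is indirect, through decisions that follow the Score.
- **Coming to favour a Score-based recommendation is part of the intended pathway.** The Background expects the question prompt list to help patients understand the rationale for the recommendation, and 2.2 does not say pre-decision. This stands in part: such movement is not plainly an artefact, but the plan cannot say whether it came before or after the decision.
- **The study is preliminary.** Feasibility is the primary objective and preference is a secondary aim. This limits the weight of the point.
- **The 95% comes from earlier work.** True, but it is the only figure the plan gives.

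**Conclusion.** The concern holds in a limited form. If the earlier experience carries over, about 71 of 75 women will give the T2 rating after deciding. The match of that rating with treatment received therefore cannot show that preferences were aligned before the choice or drove it. The match may be inflated by an amount the documents do not allow one to estimate. In the illustration, a true match of 70% would be seen as anything from 70% to 84% as the share of re-rating mismatched women runs from none to half. These shares are assumptions, and the Background's report of stable preferences favours the lower end.

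A reader might go further and infer that the Aim 2 and Aim 3 preference hypotheses would be confirmed by acceptance of the decision alone. The documents do not support that. Those hypotheses concern the Score, the route to them is indirect, and even under the assumed shifts a spurious significant result arises in no more than about half of trials, and far fewer at the smaller shift.

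**What to change.** 1. **In 6.4,** do not use the T2 preference-treatment match as evidence that preferences were aligned. Report it as consistency between decision and rating, and flag women undecided at T2, a status the interview already notes.
2. **In 2.2 and 6.4,** for the Aim 2 and Aim 3 hypotheses, define concordance as agreement of the T1 and T2 preference with Recurrence Score category. State that a T1-to-T2 rise may include post-decision change. The definition also needs to say how women with intermediate Scores are handled, since the Background describes their appropriate treatment as unclear.
3. **In the analysis text of 17.1,** report T1 preference against treatment received beside the T2 match. T1 precedes the decision but also the Score, so the gap between the two matches is not an estimate of inflation; it shows how much of the T2 agreement was already present.
4. **Also in 17.1,** report Recurrence Score category against chart-confirmed chemotherapy selection as an outcome in its own right.

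All four use data already collected and need only wording and a few extra tabulations. The cost is a weaker preference claim. Coding the preference a woman voices in the recorded encounter before the decision could be added as exploratory only: it is a different instrument from the rating scale, has no T1 counterpart, and will be missing for women who are not recorded or voice no preference.

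### The T1–T2 comprehension change covers both the QPL and Score disclosure, so in a single arm it cannot be reported as an effect of the QPL, as Aim 2 frames it

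*Combined protocol and SAP*

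**What the plan says.** Section 1.0 gives the design as "Single Arm Feasibility and Efficacy Study". Section 6.2 sets the order of events:

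- Staff "complete the first, T1 interview before the patient receives" the Oncotype DX result.
- Of the QPL it says: "They will receive the QPL by mail or email, depending on their preference, before their Score disclosure appointment".
- Finally: "The second, T2 interview will be done after patients receive their test results but prior to initiation of adjuvant chemotherapy".

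Section 6.4 describes the comprehension measure as follows: "We will assess comprehension of adjuvant treatment, Recurrence Score and category, and treatment implications". Table 1 in section 6.4 lists comprehension ("Adjuvant treatment, Recurrence Score, treatment implications") at T1 and T2, with no measurement between receipt of the QPL and disclosure. The items are not printed in full. The text says "We will apply existing comprehension items", cites a source, and gives one general-knowledge example.

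Aim 2 in section 2.1 is to "Evaluate intervention effects on comprehension and treatment preferences". The hypothesis in 2.2 and the analysis text in 17.1 both describe the expected rise as running from before to after the QPL. For Aim 2a, 17.1 fits a linear mixed model with time among its fixed effects and reports the adjusted mean change with a 95% confidence interval. It names no control group, historical comparison or benchmark. Section 3.0 says that impact will be assessed preliminarily. Neither Aim 2 nor 17.1 repeats that limit.

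**The concern.** The measure covers the subjects one would expect an oncologist to explain when disclosing a Recurrence Score: the Score, its category and what it implies for treatment. A patient who never opened the QPL could score higher at T2 because she had been to that appointment. The plan gives both exposures to everyone in the same interval, then names the change after only one of them.

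What is at stake is the conclusion the trial may draw. Comprehension change is the only outcome with a power calculation in 17.1, and the study is titled as one of efficacy as well as feasibility. A significant rise reported in Aim 2's terms would be read as evidence that the QPL works, which this contrast cannot show.

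**Working it through.** **1. Can any term in the model separate the two exposures?** 17.1 can be read as making time the main predictor, or as listing time and a main predictor separately. In a single arm measured twice, an indicator for before or after the QPL takes the same values as time, and so does one for before or after disclosure. All three are the same column. On either reading, the adjusted mean change is the change over QPL plus disclosure.

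**2. The plan's own figures (17.1).** Inputs: 75 participants at T2, 10 patients per oncologist, ICC 0.02, correlation 0.5, two-sided 0.05.

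- Design effect = 1 + (10 − 1) × 0.02 = 1.18.
- Effective N = 75 / 1.18 = 63.6, which the plan gives as 64. This reproduces.
- SD of change = SD × √(2 × (1 − 0.5)) = 1.000 SD.
- Power for 0.4 SD at N = 64 is 88% (noncentral t). The change detectable with 80% power is about 0.36 SD, so the plan's pairing of 80% with 0.4 SD fits only as a rounded figure. This does not affect the point here.

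This is power to detect any T1–T2 change, whatever caused it.

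**3. Illustration with an inert QPL.** The documents give no disclosure-only rise. I assume 0.1 to 0.4 SD, the upper end being the plan's own target. Because 17.1 does not justify the correlation, I also vary it from 0.3 to 0.7.

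The chance of a significant increase comes from the noncentral t with 63 degrees of freedom, critical value 1.998 and noncentrality shift × √64 / SD of change. The smallest significant observed rise is 1.998 × SD of change / 8.

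| Correlation | SD of change | No rise | 0.1 SD | 0.2 SD | 0.3 SD | 0.4 SD | Smallest significant rise |
|---|---|---|---|---|---|---|---|
| 0.3 | 1.183 | 2.5% | 9.8% | 26.5% | 51.5% | 75.9% | 0.296 SD |
| 0.5 | 1.000 | 2.5% | 12.1% | 35.0% | 65.7% | 88.3% | 0.250 SD |
| 0.7 | 0.775 | 2.5% | 17.3% | 53.0% | 86.2% | 98.2% | 0.193 SD |

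A clustered simulation at correlation 0.5 (75 patients, 8 oncologists, ICC 0.02 on the change, 20,000 replicates) gave 2.6%, 12.3%, 34.9%, 66.1% and 88.7%, in line with the middle row.

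At the plan's figures, any observed rise of about 0.25 SD or more is significant, whatever mix of QPL and disclosure produced it.

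**The case against.** The strongest reply is that this is a declared single-arm feasibility study. Feasibility is the primary objective, section 3.0 promises only a preliminary assessment, and the QPL is meant to work through the disclosure visit, so T2 has to come after it. All of that stands and lowers the weight of the point. But a preliminary label speaks to strength of evidence. It does not tell the reader that the estimate combines two exposures. Aim 1 fidelity data and the Aim 3 encounter coding inform on mechanism, but neither supplies a disclosure visit without the QPL.

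Some stronger readings are tempting, and the documents do not support them:

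- *That 17.1 itself claims an intervention effect, or that a decision hangs on the test.* 17.1 speaks only of an adjusted mean change, under a label that refers to the QPL. The explicit attribution is in Aim 2, and no success or go/no-go rule is tied to the result.
- *That the rise is partly built in because patients cannot know their own Score at T1.* The items are not shown, the printed example could be answered at T1, and the separate Recurrence Score row in Table 1 is T2 only. Such items may not exist.
- *That the percentages are this trial's false-positive rate.* They are a power curve under assumed shifts. Section 3.0 also notes that many women understand their Score poorly, which may mean that usual disclosure raises comprehension little.
- *That preferences are affected equally.* They span the same interval, but section 3.0 reports that in the team's earlier data preferences did not shift after the Score. That makes disclosure a weaker rival explanation, although 17.1 does not use those data as a comparison.

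**Conclusion.** The point holds, as one about what the Aim 2 estimate means. The timeline, the single arm and the two measurement times are explicit, and from them it follows without further assumption that the T1–T2 change is the joint change over QPL plus disclosure. Aim 2's wording goes beyond that.

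The size of the disclosure part is unknown. The 12% to 88% range at the plan's figures rests on assumed shifts of 0.1 to 0.4 SD and shows only that a modest disclosure-only rise could produce a significant result. It is not evidence that this will happen. The concern is smaller for preferences than for comprehension. It should be fixed because the correction is nearly free and changes what the trial can conclude. It does not touch the feasibility objective.

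**What to change.** In 2.1, 2.2 and 17.1, define the Aim 2 comprehension estimate as the adjusted mean change from T1, before the QPL, to T2, after both the QPL and Score disclosure. State that a significant rise will not be reported as an effect of the QPL.

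Use the same wording for the Score-concordant preference hypothesis. Note beside it that the team's earlier data showed no preference shift after the Score, so the concern is smaller there.

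As a conditional safeguard only, check the cited comprehension items. If any asks for the patient's own Score or category, mark it in 6.4, leave it out of the T1–T2 change score, and report it at T2 as percent correct with a 95% confidence interval. This would remove a built-in rise if there is one. It would not separate QPL from disclosure, because the visit can raise general-knowledge items too.

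The cost is text in 2.1, 2.2, 6.4 and 17.1, with no added visits or data. The downside is a more modest conclusion for a secondary aim and, only if own-result items exist, a slightly shorter change scale.
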